1.1 Specific aims of the study

Black men who have sex with men (BMSM) suffer from alarmingly high rates of HIV in the United States^{1,2}. The most recent statistics indicate that BMSM are 550% more likely to be diagnosed with HIV than white MSM (WMSM)^{1,2}. Pre-exposure prophylaxis (PrEP) reduces risk of HIV infection by 92%³, yet profound racial disparities in the uptake of PrEP persist. In 2015, among those offered PrEP, only 10% of blacks compared to 75% of whites used PrEP⁴. Low PrEP uptake in BMSM is driven by: *poor access to PrEP* including inconvenient locations of PrEP-prescribing physicians⁵⁻¹⁰ and *distrust of physicians and stigma*, which limit communication about PrEP and its side effects^{6,11}. According to Cohen's structural theory improving access to PrEP will improve PrEP uptake¹². Since HIV among BMSM is largely clustered in high poverty, racial minority neighborhoods^{13,14}, we can improve access by directing PrEP delivery to these areas. Pharmacists in these neighborhoods have strong rapport with the residents¹⁵ and as a trusted source for health information, could effectively inform BMSM about PrEP. Our work indicates that offering HIV prevention services in pharmacies located in high poverty, racial minority neighborhoods is feasible¹⁶ and can reduce stigma because pharmacies offer a host of less stigmatized health services (e.g. vaccinations)¹⁸. Moreover, preliminary data among BMSM show strong support for obtaining PrEP in pharmacies.

The purpose of this study is to develop a culturally appropriate pharmacy PrEP delivery model for BMSM who live in high poverty, racial minority neighborhoods. Pharmacies have proven to be a feasible source for offering PrEP for WMSM^{17,18}, but have failed to reach the most at-risk, vulnerable population – BMSM¹⁹. State regulations limit pharmacists' ability to screen and prescribe PrEP in 21 states, so many pharmacies use nurse practitioners (NPs) instead¹⁸. But, pharmacies in high poverty, racial minority neighborhoods often lack NPs. Thus, we have designed a multi-level intervention that does not rely on pharmacists or NPs to screen BMSM for PrEP. Increasing PrEP access and uptake will reduce HIV incidence and racial inequities in HIV, two NIH HIV/AIDS high priority areas. This protocol describes the aims of this study, which are to:

Aim 1. Develop a pharmacy PrEP delivery model by evaluating the barriers to and facilitators of integrating PrEP into existing pharmacy practice among key stakeholders (pharmacists, technicians, PrEP-prescribing physicians and BMSM).

Aim 2. Evaluate eligibility and willingness to receive PrEP in pharmacies among BMSM and collect data on customer engagement with PrEP delivery information from pharmacy staff during COVID-19.

Aim 3. Pilot test the pharmacy PrEP delivery model and examine its feasibility, acceptability and safety, and gather early evidence of its impact and cost with respect to PrEP uptake at baseline and at 3-months (the clinically suggested follow-up period) among pharmacy client participants.

1.2 Background and preliminary studies that support this stage of research

BMSM bear the highest burden of HIV in the US. Between 2005 and 2014, HIV diagnoses increased 22% for BMSM but declined 19% for WMSM^{1,2}. In Georgia, blacks make up less than 40% of the population

but represent 74% of new AIDS diagnoses. And almost two-thirds of incident HIV infections were among blacks via male-male sex²⁰.

PrEP is the single most effective HIV prevention strategy yet under-utilized among BMSM. When taken every day PrEP can prevent up to 92% of HIV infections^{3,19}. Studies estimate that 48-70% of BMSM are willing to use PrEP^{5,21}. Yet, uptake among blacks remains low (~10%)⁴. Lower insurance rates among blacks compared to whites²² may be a barrier to PrEP. But, evidence of comparable insurance rates among BMSM and WMSM²³, as well as prescription payment programs that cover most or all of the costs of PrEP do not completely explain significant disparities in PrEP uptake²⁴. Indeed, limited access to PrEP, distrust of physicians and stigma are noted as critical barriers to PrEP that must be improved to reduce HIV^{5,21}.

Neighborhood residence shapes BMSM HIV exposure and access to HIV prevention resources¹³. A recent study showed that 60% of prevalent HIV cases were located in one central Atlanta cluster¹⁴. Census tracts with high HIV had 20% higher poverty and 200% larger MSM populations. High poverty neighborhoods also have the fewest HIV physicians^{10,25,26}. While most census tracts are within 15 minutes of an HIV physician by car, residents in HIV prevalent areas have low rates of car ownership and commute time more than doubles when traveling by public transportation¹⁰, which is unavailable in some areas.

There is a strong scientific premise for increasing PrEP delivery in pharmacies for BMSM. About 95% of Americans live within 5 miles of a pharmacy; pharmacies have flexible hours and pharmacists have high credibility with community members¹⁵. Studies have shown pharmacies can engage with high risk populations including people who inject drugs (PWID) to reduce HIV risk behaviors²⁷⁻³⁰ and provide primary prevention services including immunizations³¹, blood pressure screenings³² and HIV testing^{16,33-35}. PrEP has also been sustainably offered in a Seattle pharmacy, but mostly to white MSM (85%). Nevertheless, almost 100% initiated PrEP and 75% followed up for continued PrEP¹⁷. Following this, 188 Walgreens across the US have offered PrEP through their existing clinics^{18,36}.

Existing pharmacy PrEP models have limited potential for reaching BMSM. In Seattle, state regulations give pharmacists authority to administer biological screenings (HIV, STI and creatinine) and prescribe PrEP¹⁹. Many states do not have legislation that expand pharmacists' purview in service delivery^{37,38}. Walgreens has overcome this regulatory limitation by using nurse practitioners to screen and prescribe PrEP in their existing clinics¹⁸. While Collaborative Practice Agreements between pharmacists and physicians are another route to deliver services through pharmacies^{39,40}, they are time-consuming and thus infeasible for community pharmacists in high morbidity neighborhoods who already have a hectic workflow; and for chain pharmacies these partnerships are determined on a corporate rather than individual pharmacy level⁴⁰⁻⁴³.

1.3 Significance/ justification for the current study

The contribution of the proposed research is expected to be a sustainable, pharmacy PrEP delivery model that can be implemented without regulatory barriers to increase PrEP access in high poverty, racial minority neighborhoods for BMSM who have the highest need. *This contribution will be significant because it will lay the foundation for making PrEP available in pharmacies specifically for populations that are disconnected from HIV prevention resources.*

2. Design

To accomplish these aims, we will conduct a four-phase study:

- (1) **formative phase** of in-depth interviews and workflow assessments among 40 key stakeholders to inform phase two.
- (2) **intervention development phase** to integrate formative data with input from an existing advisory board to develop a culturally relevant pharmacy PrEP delivery model.
- (3) **transitional pilot phase** to assess customer eligibility and willingness to receive PrEP in pharmacies during COVID-19.
- (4) **pilot test phase** to test the model in two pharmacies in high poverty, racial minority neighborhoods, where we have existing relationships.

For the remainder of the protocol, we will describe the methods according to each phase of the study.

2.1 Sample

This study will include various participant groups across each phase of the study. For clarification in terminology of each type of participant, here we provide definitions of each group:

Pharmacist – Pharmacist participant

Technician – Pharmacy technician participant

Pharmacy staff – Pharmacist, pharmacy technician and pharmacy clerk participant

Client – Pharmacy client participant who patronizes pharmacy enrolled in the study

In the formative phase, we will collect data from key stakeholders: 10 pharmacists, 10 technicians, 10 PrEP-prescribing physicians and 10 black men who have sex with men (BMSM) via in-depth interviews. Interviews will assess support for PREP screening, referral and monitoring in pharmacies, pharmacy-level policies influencing PrEP provision, potential barriers to the delivery of an intervention in a pharmacy, existing interactions between pharmacists and physicians, advocacy resources, knowledge of epidemiologic data on HIV, sexual behavior, drug use and PREP, and sustainability through pharmacy-physician-community collaboration. We will also perform workflow assessments among pharmacists, technicians and PrEP prescribing physicians to examine the facilitators and barriers to PrEP implementation.

In the intervention development phase, *there are no pharmacy staff or client participants, thus no data protections are needed.* In this phase of the study the investigative team and advisory board will use the data analyzed from the formative phase to develop the pharmacy PrEP delivery model to be implemented in the pilot study. We will also iteratively revise the protocol over the course of the study to ensure its feasibility, acceptability, and safety. We will debrief about the study activities **every month** of the pilot study to refine the protocol for immediate implementation in the study activities. Each proposed change will be assigned a subject matter expert from the co-I's on the grant. The subject matter expert and at least two other co-I's will be asked to vote on whether the change will be made immediately, revoked or followed through the next monthly meeting. Any change that requires the recruitment, protocol or survey instruments to be revised will be submitted to the IRB for approval. Meticulous records of the development and revision process of the pharmacy PrEP delivery model will be kept throughout the study.

In the transitional pilot phase, two pharmacies will be chosen to estimate how many pharmacy client participants would be eligible for the pilot phase. Among those who would be eligible, we will assess their willingness to receive PrEP in pharmacies. In order to recruit a sample of pharmacy client participants, pharmacy staff participants will place flyers in pharmacy client participants' medication delivery packages and hang posters in their pharmacies. Given the COVID19 pandemic, many client participants are opting for medication delivery versus in-person pick up. The flyers and posters will contain information about the pharmacy-based PrEP delivery study. A QR code will allow client participants to be directly linked to the eligibility screener. After taking the eligibility screener, client participants will be eligible for the social and behavioral survey if they are: 1) male or trans male, 2) had any types of sex in the past 6 months, 3) engaged in unprotected sex in the past 6 months, 4) had protected and/or unprotected sex with HIV positive partners in the past 6 months, and 4) injected any drugs in the past 6 months. We will ask pharmacy staff to insert flyers into patient medication deliveries over a 3-month period and during this time we will assess pharmacy staff barriers and facilitators of engaging with client participants regarding the study.

In the pilot test phase, two pharmacies will be chosen to pilot test the pharmacy PrEP delivery model. We will recruit pharmacy staff participants who work in each pharmacy and pharmacy client participants that patronize these pharmacies. Pharmacy staff participants will complete a pharmacy-based HIV prevention training to equip them with the tools needed for optimal PrEP delivery. Since the pharmacies selected to be a part of the study are located in racial minority neighborhoods, we anticipate that most client participants will be racial minorities. We will be collecting both qualitative and quantitative data to assess the impact of the pharmacy PrEP intervention on the pharmacy environment, personnel, and business flow. Among the pharmacy client participants, we will assess feasibility, acceptability and safety of the intervention activities, satisfaction with the activities and participation in activities without stigmatization, discomfort, or harm.

Pharmacy client participants will be considered eligible for the social behavioral survey if they:

- Consent to participate in the online screener
- Are 18 years or older
- Can speak and read English without any help

In accordance with current CDC guidelines, Pharmacy client participants will be considered eligible for HIV testing if answers from the social behavioral survey indicate that:

- They consent to participate in the social behavioral survey
- They are willing to be tested for HIV today

Respond "yes," "don't know," or "prefer not to say" to one or more of the following conditions:

- Identify as male, trans female, gender-non-conforming," or "other" and reports having sex with men within the past 3 months
- Having vaginal or anal sex without a condom within the past 3 months
- Having ever used injectable drugs

Pharmacy client participants will be considered ineligible for HIV testing if they do not consent to partake in the social behavioral survey, do not consent to be tested for HIV, or answer "yes" to both of the following conditions:

- Reports no vaginal or anal sex without a condom within the past 3 months **and** identifies as a woman or trans male who has not had sex without a condom within the past 3 months
- Has never used injectable drugs

Pharmacy client participants will be eligible for a 30-day supply of PrEP from the pharmacy if they:

- Test negative for HIV
- Agree to receive medication from the pharmacy

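### The transitional screener's gender item conflicts with the pilot's eligibility rule, so the count of pilot-eligible clients leaves out groups that the pilot can admit

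*Combined protocol and SAP*

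**What the plan says.** **Purpose.** Section 2.1 says of the transitional phase that "two pharmacies will be chosen to estimate how many pharmacy client participants would be eligible for the pilot phase". It continues: "Among those who would be eligible, we will assess their willingness to receive PrEP in pharmacies".

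**Transitional screener (Section 2.1).** The rule reads "client participants will be eligible for the social and behavioral survey if they are: 1) male or trans male". Any sex and unprotected sex, both in the past 6 months, follow. The list ends "had protected and/or unprotected sex with HIV positive partners in the past 6 months, and 4) injected any drugs in the past 6 months". Two items carry the number 4, and the items are joined by *and*. The protocol gives no other definition of a client who would be eligible for the pilot.

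**Pilot rule (Section 2.1).** Survey entry needs consent, age 18 or over, and English. HIV testing, the step that leads to PrEP supply, needs consent, willingness to be tested that day, and at least one of three conditions:
- "Identify as male, trans female, gender-non-conforming" or other, with male partners in the past 3 months;
- "Having vaginal or anal sex without a condom within the past 3 months";
- ever having injected drugs.

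The ineligibility rule pairs never having injected with a condition covering a client who "identifies as a woman or trans male who has not had sex without a condom within the past 3 months".

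**Target population.** Aim 2 (Section 1.1) and the first transitional step in Section 2.4 refer to BMSM. Section 2.3 says the flyers are to inform men. Section 2.1 speaks of pharmacy clients without restriction, and Section 2 of customers.

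**The concern.** The screener is the only instrument for the eligibility count, and willingness is measured only in those it passes. Its gender item is not the pilot's. In the pilot, gender appears in one of three alternative conditions and in the ineligibility rule; it is not a bar to entry. The trans categories are also reversed. The screener admits trans men and omits trans women. The pilot's sex-with-men condition names trans women and omits trans men.

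At stake is whether the count can be read as a forecast of pilot-eligible clients. Willingness data not collected from the omitted groups cannot be recovered at analysis.

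**Working it through.** The plan states no expected eligible share or sample size for this estimate, so there is no figure to reproduce. The check applies both rules to the same set of logical cases.

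**Step 1: the cases.** The inputs are the items in the two Section 2.1 lists: male partners in 3 months; condomless sex in 3 and in 6 months; any sex in 6 months; HIV-positive partner in 6 months; injection ever and in 6 months. Only consistent combinations are kept.
- No sex in 6 months: 3 injection histories (never, earlier, within 6 months) = 3.
- Sex in 6 months: 2 (male partner) × 3 (condomless: none, 3–6 months ago, within 3 months) × 2 (HIV-positive partner) × 3 (injection) = 36.
- Total: 3 + 36 = 39 per gender category.

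These are unweighted cases, not prevalences. Answers of don't know or prefer not to say, which the pilot accepts as qualifying, are not modelled.

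**Step 2: pilot-qualifying cases.**
- Male, trans female, gender-non-conforming, other: a case fails only if never injected, no condomless sex in 3 months and no male partner. That is 1 + 2 × 2 = 5 cases, so 39 − 5 = 34 qualify.
- Women and trans men: the male-partner condition does not apply, so 1 + 2 × 2 × 2 = 9 fail and 39 − 9 = 30 qualify.

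**Step 3: pilot-qualifying cases that the screener scores ineligible.**

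| Reading of the screener list | Women | Trans women, gender-non-conforming, other (each) | Men | Trans men |
|---|---|---|---|---|
| (a) All items required, as written | 30/30 | 34/34 | 30/34 | 26/30 |
| (a) with gender item removed | 26/30 | 30/34 | 30/34 | 26/30 |
| (b) Gender, any sex, and at least one risk item | 30/30 | 34/34 | 5/34 | 4/30 |
| (b) with gender item removed | 4/30 | 5/34 | 5/34 | 4/30 |
| (c) Any one item suffices | 1/30 | 1/34 | 0/34 | 0/30 |

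Under (a) and (b) every qualifying case in the omitted groups is lost. Under (b) gender is the main cause. Under (a) most cases stay lost after gender is aligned, because all items are required. Under (c) gender excludes nobody; the one lost case is a client who injected more than 6 months ago and has had no sex in 6 months.

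**Step 4: errors in the other direction.** Under (b) the screener also passes 3 male and 6 trans male cases that fail the pilot rule; under (a) it passes none. The gender item's own effect is downward, but under (b) the other differences can partly offset it.

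**Step 5: size.** If all other items matched and a share *f* of pilot-qualifying clients belonged to the omitted groups, the count would capture 1 − *f*: 0.9 at *f* = 0.1, 0.7 at *f* = 0.3, 0.4 at *f* = 0.6. The documents give no gender mix, so *f* is an assumption throughout.

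**The case against.** The strongest defence is that the phase was meant for BMSM. Aim 2 and Section 2.4 say so, the flyers address men, and Section 2.11 analyses pilot client data among BMSM. This stands as far as women are concerned. A reader might infer that omitting women makes Aim 2's estimate wrong; as Aim 2 is worded, women are outside its target, and their omission bears only on Section 2.1's count of clients. The defence does not explain the trans categories: the listed criteria include neither race nor sex with men, and they admit trans men while leaving out trans women, whom the pilot places alongside men with male partners.

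Other limits also stand:
- **Gender must be required.** A reader might infer that the joining of the items is immaterial. It is not: under reading (c) the gender item excludes nobody. The list is garbled enough that intent is uncertain, although (c) is not what it says.
- **The comparator is inferred.** The screener list gates a survey, while the pilot's three conditions gate HIV testing. But pilot survey entry has no gender criterion at all, so the mismatch remains on either comparison.
- **No percentage is supportable.** Assume women are 40–60% of clients, with qualifying rates of 40–80% in men and 40–60% in women. The missed share then runs from 0.16/(0.16 + 0.48) = 25% to 0.36/(0.36 + 0.16) = 69%. None of these inputs is in the documents, and the range says nothing about trans or gender-non-conforming clients.
- **Not every discordant case is about gender.** A trans man whose only risk is condom-protected sex with an HIV-positive partner passes the screener and fails the pilot rule. So does a cisgender man with no male partner in the past 3 months and the same history. The HIV-positive-partner item causes this.
- **The consequence is limited.** The sample is self-selected by QR code and the analysis mainly descriptive. No go/no-go rule uses the count, and the pilot's n=60 is not derived from it.

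**Conclusion.** The conflict is real and nothing in the protocol reconciles it. With gender as a required item, the screener scores as ineligible all pilot-qualifying trans women, gender-non-conforming and other clients, and women, and asks none of them about willingness. The gender item therefore biases Section 2.1's client count downward by an unknown amount. For Aim 2 as worded, the error is confined to the trans and gender-non-conforming categories.

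The conclusion rests on two readings: that the survey gate also defines who would be eligible for the pilot, and that gender is mandatory. Gender is one of several differences. The protocol also differs on *and* versus any one condition, 6 versus 3 months, injection in 6 months versus ever, and an HIV-positive-partner item found only in the screener. The point deserves correction because the rule as written gives a wrong count and the repair is cheap.

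**What to change.** 1. Record gender in the transitional screener with the pilot's categories.
2. Collect there every item the pilot conditions use: sex with men and condomless sex in the past 3 months, and ever having injected. Add race if the form does not already ask it, so that BMSM can be identified.
3. Derive a flag for would be eligible for the pilot in all screener completers, using the pilot's any-one-condition rule. State that it covers the gender and behavioural conditions only, not willingness to be tested that day.
4. Report the flag by gender and separately for BMSM.
5. Reconcile Sections 1.1, 2.1, 2.3 and 2.4 on which population the estimate covers, and carry that statement into Section 2.11.

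Swapping the gender list alone would not give a valid flag, for the reasons in the verdict. None of this changes the pilot's own rule for testing or supply.

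**Cost.** A few added screener items and one derived variable. The flag repairs the count only. Measuring willingness in the wider group means surveying it, at $25 per additional survey; otherwise the report should state that willingness covers only the surveyed group.

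### As printed, the transitional-pilot survey gate requires all five items, so it admits only recent injectors and excludes every Black MSM who has never injected; its connector and link to pilot eligibility need stating

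*Combined protocol and SAP*

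**What the plan says.** Section 2.1 (Sample) gives the transitional pilot two purposes. First, "two pharmacies will be chosen to estimate how many pharmacy client participants would be eligible for the pilot phase". Second, "Among those who would be eligible, we will assess their willingness to receive PrEP in pharmacies". Aim 2 in section 1.1 names the same two outputs, eligibility and willingness, among Black MSM.

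Clients reach the social and behavioural survey through an eligibility screener. Section 2.1 lists the entry items: male or trans male; any sex; unprotected sex; and then "had protected and/or unprotected sex with HIV positive partners in the past 6 months, and 4) injected any drugs in the past 6 months". The three middle items and the last each carry a 6-month window. The number 4 is used twice, and *and* is the only connector. Sections 2.2 and 2.4 say that those found eligible are then prompted to take the survey. They do not restate the items.

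The pilot's eligibility lists, also in section 2.1, have three tiers: entry to the survey (consent, age 18 or over, English), HIV testing, and a 30-day PrEP supply. HIV testing requires survey consent, "They are willing to be tested for HIV today", and a qualifying answer "to one or more of the following conditions". The conditions are:

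- on male partners, a listed gender identity "and reports having sex with men within the past 3 months";
- on condom use, for any gender: "Having vaginal or anal sex without a condom within the past 3 months";
- on injecting, with no time window: "Having ever used injectable drugs".

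Answers of not knowing or preferring not to say also qualify. Section 2.11 plans sexual behaviour and substance use among the correlates for the transitional data.

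**The concern.** A phase meant to describe who would be eligible for the pilot, and how willing they are, uses an entry rule built differently from the pilot's. One rule demands everything on its list; the other demands any one thing on a different list with different time windows.

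Three things are at stake if the screener follows the printed text.

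- **Willingness.** Only people sent to the survey can give survey data on willingness. Those screened out cannot be added back at analysis.
- **Target population.** Aim 2 concerns Black MSM. The gate has no item on sex with men, and as printed it turns on injecting drug use.
- **Planned correlates.** Every respondent would have answered yes to the same four behaviour questions. As yes/no variables these could not be correlates of anything. Frequency, partner numbers, non-injection drug use, insurance and HIV-testing history could still vary.

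**Working it through.** The plan gives no sample size, rate or power for this survey, so there is no figure to reproduce. The check is logical, with both rules taken from section 2.1.

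| Element | Transitional survey gate (as printed) | Pilot rule for HIV testing (behavioural part) |
|---|---|---|
| Connector | all items | any one condition |
| Gender | male or trans male | restricts only the sex-with-men condition |
| Sex with men | not asked | 3 months |
| Any sex | 6 months | not asked |
| Unprotected or condomless sex | 6 months | 3 months, vaginal or anal |
| HIV-positive partner | 6 months | not asked |
| Injecting | 6 months | ever |
| Non-answers | not stated | count as qualifying |

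**Step 1: is the gate inside the pilot rule?** Anyone who passes has injected in the past 6 months, so has ever injected, so meets the third pilot condition. Every passer therefore meets the behavioural rule. The nesting rests on this item alone. Without it the 6-month and 3-month windows would break it.

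**Step 2: is the pilot rule inside the gate?** No. A Black man who has had condomless anal sex with men in the past 3 months and has never injected meets two pilot conditions and fails the gate. The subset is strict.

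**Step 3: ceiling.** Passing requires every item, so

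share passing ≤ smallest share among the items ≤ share who injected in 6 months.

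Among Black MSM who have never injected, the share passing is exactly 0.

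**Step 4: illustration on assumed rates.** The documents give no prevalences. Assume, for men: unprotected sex u = 30% to 70%, HIV-positive partner h = 5% to 30%, injecting i = 2% to 20%, sex with men m = 5% to 50%. Treat these as independent, ignore the difference in windows, and use i for ever injecting too.

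- Gate: u × h × i = 0.30 × 0.05 × 0.02 = 0.03% at the low end; 0.70 × 0.30 × 0.20 = 4.2% at the high end.
- Pilot rule: 1 − (1 − m)(1 − u)(1 − i) = 1 − 0.95 × 0.70 × 0.98 = 35% at the low end; 1 − 0.50 × 0.30 × 0.80 = 88% at the high end.
- If the risks overlap completely, the gate rises to its rarest item and no further: 2% to 20%.

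**Step 5: the other natural reading.** Suppose male or trans male plus any one behaviour was meant. A man with sex with men in the past 3 months has had sex in the past 6 months, so he passes. The mismatch for men is then small, but it remains:

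- A man who has never injected, and has had no sex with men and no condomless vaginal or anal sex in 3 months, passes if he had any sex in 6 months. He does not meet the pilot rule.
- A man whose only qualifying fact is injecting more than 6 months ago, with no sex in 6 months, meets the pilot rule and is missed.

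Changing the connector alone does not make the two rules agree.

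**The case against.** The strongest reply is that the *and* is a slip. Under it, the any-sex item is redundant because unprotected sex implies it. Mentioning protected sex with HIV-positive partners is pointless if unprotected sex is already required. The number 4 appears twice. The screener itself is not in the documents, so nobody can say that the strict rule was programmed. This stands, and it makes the large harm conditional. It does not remove the point: no section supplies the intended connector, a screener must be built on some rule, and step 5 shows that the looser reading does not match the pilot rule either.

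Second, Aim 2 is descriptive, no stated decision depends on the count, and section 2.4 already gives n=60 for pilot clients. This also stands. The damage is to Aim 2's own result, not to the sizing of the pilot.

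A reader might infer more than the documents support:

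- **That the number passing is the plan's estimate of pilot eligibility, or a lower bound on it.** Section 2.1 calls the items the gate to the survey and never equates passing with pilot eligibility. Section 2.6 has the screener and survey together determine behavioural eligibility for PrEP.
- **That the gate is a subset of full pilot eligibility.** It is not shown to be: age, English and willingness to be tested that day are not among the five items.
- **That counts of answer patterns measure the loss.** Take men with sex with men in 3 months. Three states of condomless sex (none in 6 months, 3 to 6 months ago, within 3 months), two of HIV-positive partner and three of injecting give 3 × 2 × 3 = 18 patterns, of which 2 × 1 × 1 = 2 pass. Splitting condomless sex by whether it was vaginal or anal gives 5 × 2 × 3 = 30 patterns, of which 4 pass. The fraction moves with the coding, and patterns are not people.

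**Conclusion.** The concern holds as a conflict between two rules in section 2.1. As printed, the survey gate is a strict subset of the pilot's behavioural rule for HIV testing, and it shuts out every Black MSM who has never injected. Neither conclusion needs an assumption about prevalence or about what unprotected means.

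The size in people cannot be stated from the documents. The firm bound is the share of clients who injected in the past 6 months; the percentages in step 4 rest wholly on assumed rates.

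This should be fixed, with the severity conditional on the *and* reading. If it is applied, the willingness result from the survey does not describe Aim 2's population. If any one behaviour was meant, what remains is a small mismatch for men in windows and items, plus an undefined pilot tier.

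**What to change.** Reconcile the transitional gate with the pilot's HIV-testing rule in section 2.1. This review takes no position on which criteria are right.

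1. Write out the connector and correct the numbering.
2. State which pilot tier eligibility refers to: survey entry, HIV testing or PrEP supply.
3. Have the transitional screener ask the items of the reconciled rule, with its look-back windows.
4. Send everyone who meets that rule to the survey, so that willingness is measured in the stated denominator.

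The cost is reprogramming a 3-minute online screener and an IRB amendment. If the strict gate is already in use, more clients will qualify for the $25 survey payment, so incentive spending rises.
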